#### 2.1 Methotrexate Pharmacokinetics

The pharmacokinetics of methotrexate vary greatly among patients, with a fixed dose resulting in a 7-fold variation in the range of plasma concentration. This variability can also exist in individual patients on subsequent administrations of HDMTX. Therapeutic drug monitoring has thus become a standard part of protocols in patients receiving HDMTX.

Typically pharmacokinetics of HDMTX are described using a two compartment model with four parameters (CL – clearance, V1 – central compartment volume of distribution, V2 peripheral compartment volume of distribution, and Q – intercompartmental clearance). Clearance (CL) of MTX ranges from 3.5-7.1 L/h, and is inversely proportional to the age of the patient. Among patients with the same total bodyweight (TBW), MTX clearance was 30% higher in children less than 10 years when compared with children greater than 10 years of age. The volume of distribution of central compartment ( $V_1$ ) is 45% of TBW regardless of age.

The variation in pharmacokinetics also has important clinical implications. Prospective pharmacodynamic studies of patients with ALL receiving HDMTX have shown that those patients with median MTX plasma concentration at steady state ( $Cp_{ss}$ ) less than  $16\mu M$  had significantly lower rates of remaining in remissions compared to patients with  $Cp_{ss}$  greater than  $16\mu M^5$ .

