Based largely on the previous work at SJCRH, we developed an individualized methotrexate treatment plan as an option to safely administer HDMTX, with a target Cpss of 65 μM to patients at risk for delayed clearance and subsequent toxicity. Other options for this population would include a 25% methotrexate dose reduction or complete omission of HDMTX from their treatment. Since 2007. Texas Children's Hospital (TCH) has given patients with past history of toxicities including renal toxicities individualized methotrexate with no known increase in toxicities based on evolving versions of this treatment plan (n =14 patients; ref: personal communications with faculty members of the Texas Children's Hospital Leukemia Program). Work by Aumente, et al, demonstrated that the Monte Carlo simulated MTX concentration and means over time show a peak methotrexate concentration near hour 2, with steady state occurring near hour 6. Therefore, our treatment plan provides guidelines for HDMTX dose adjustments based on hour 2 and 6 methotrexate levels. In addition, these adjustments are based on a fixed, simple bed-side algorithm and thus avoid the need for complex pharmacokinetic modeling. Patients treated according to the algorithm may thus not need their dose altered. With this in mind, in addition to our eligibility criteria we will allow attendings to enroll patients as they deem necessary, since if the MTX Cpss is therapeutic no alterations to therapy will be made. In September, 2012, this treatment plan was formalized and approved for clinical use by the Texas Children's Cancer Center Chemotherapy Safety Committee.

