### 5.4 Laboratory Tests During Treatment

- Methotrexate levels and creatinine at times 2, 6 (or 8) and 24 hours are required for research purposes. Additional methotrexate levels and creatinine should be performed per institutional standards. Methotrexate levels and creatinine at hours 36 (if methotrexate levels are ≥150 micromolar), 42, 48 and every 6-12 hours thereafter until methotrexate is considered cleared (e.g. ≤0.4 micromolar at hour 48 and/or <0.1 micromolar thereafter) is highly recommended but considered optional. An example of routine post-methotrexate monitoring is outlined in Appendix B.

- The following labs should be drawn at Week 1 and Week 2 and repeated weekly until
  either the next dose of HDMTX is administered or 4 weeks have passed since the last
  dose of HDMTX: CBC, Creatinine, BUN, AST, ALT, total and direct bilirubin.

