### 5.6 Other information to be collected

- Ordered HDMTX dose
- date/time of 24hr infusion start
- initial HDMT infusion rate with HDMTX concentration
- date/time of each change in HDMTX infusion rate and rate at which new infusion is set (if applicable)
- date/time of 24hr infusion start and stop for concomitant medications
- date/time of completion of HDMTX infusion
- toxicities experienced during infusion,
- hour at completion of monitoring
- total MTX given
- total leucovorin given
- all MTX levels resulted and time each MTX level was drawn.

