- 1b) Explore potential changes in incidence of success (achieving an end infusion peripheral blood MTX concentration between 50-80  $\mu$ M) between sequential administrations of HDMTX. The primary endpoint and sample size calculation refer to the first cycle for each patient.
- Aim 2 2a) Calculate the frequency of adverse effects after each infusion. Success rate over multiple cycles within individual patients will be analyzed using generalized estimating equations for binary outcomes. This method will also be applied to the frequency of adverse events and to the assessment of factors associated with outcome. Continuous and ordinal/non-normal adverse effects will be compared via paired t-test or Wilcox sign rank test respectively.
- 2b) Describe the genotype of various methotrexate metabolizing SNPs in each subject. The polymorphisms of subjects in this study will be compared to published minor allele frequencies and when appropriate will be stratified by race/ethnicity. The purpose of this analysis will be to describe trends away from the major allele frequency in patients known to either have experienced or who are at high risk for developing adverse effects to HDMTX.
- 2c) Examine predictors of success of achieving a  $CP_{ss}$  of 50-80  $\mu$ M. Variables in our analysis will include (but not be limited to) age, sex, disease type, race/ethnicity and measure of pre-MTX renal function. An analysis both with and without SNP genotype will be performed secondary to the likelihood that race/SNP correlations will interfere with SNPs being a truly independent variable. We will initially use chi-square test for group variables and t-test for continuous variables. Logistic regression will be used for multivariable analysis to control for confounders and estimation of adjusted odds ratios. P<0.05 will be considered statistically significant.

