#### Analysis:

Aim 1a) Overall change in the incidence of success with the new protocol (achieving end infusion MTX levels  $50-80\mu M$ ) and

- 1b) change in incidence of success at various infusion times during interim maintenance and interim maintenance-like cycles in which patients are administered HDMTX every 2 weeks, as well as
- 1c) Success rate over multiple cycles within individual patients will be analyzed using generalized estimating equations for binary outcomes. This method will also be applied to the frequency of adverse events and to the assessment of factors associated with outcome. Continuous and ordinal/non-normal adverse effects will be compared via paired t-test or wilcox sign rank test respectively.

Aim 2) To examine predictors of success (achieving CPss of 50-80µM) we will initially use chi-square

test for grouped variable and t-test for continuous variables. Logistic regression will be used for multivariable analysis to control for confounders and estimation of adjusted odds ratios. P<.05 will be considered statistically significant.

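### Aim 1b looks for change across sequential infusions only through a two-sided success indicator, which carries no direction and is insensitive to moderate shifts near the 65 µM target

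*Combined protocol and SAP*

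**What the plan says.** Section 9.1, Aim 1b, is to "Explore potential changes in incidence of success (achieving an end infusion peripheral blood MTX concentration between 50-80" µM) from one HDMTX administration to the next. The Analysis part of section 9.3 repeats the aim as "change in incidence of success at various infusion times during interim maintenance and interim maintenance-like cycles" and gives the method: "Success rate over multiple cycles within individual patients will be analyzed using generalized estimating equations for binary outcomes".

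Methods for continuous outcomes are named for adverse effects: "Continuous and ordinal/non-normal adverse effects will be compared via paired t-test or Wilcox sign rank test respectively". The predictor analysis uses t-tests for continuous predictors, but its outcome is again the success indicator. Nowhere do the documents plan a summary, plot or model of the numeric 24-hour level by infusion.

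The level is available. Section 5.4 states "Methotrexate levels and creatinine at times 2, 6 (or 8) and 24 hours are required for research purposes", and section 5.6 lists "all MTX levels resulted and time each MTX level was drawn", along with rate changes and the total methotrexate given. Section 2.4 describes a treatment plan "with a target Cpss of 65" µM, the midpoint of the window. Section 2.1 says of methotrexate pharmacokinetics: "This variability can also exist in individual patients on subsequent administrations of HDMTX".

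**The concern.** The window is two-sided and centred on the target. When the mean level moves across the centre, failures on one side are exchanged for failures on the other, and the success rate may hardly move. A patient going from 52 to 78 µM counts as unchanged, and so does one going from 85 to 120 µM.

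The two kinds of failure mean different things here. Section 2 ties toxicity to exposure, and patients are enrolled because of their toxicity risk. The tables in section 4.1 contain rate reductions only. A drift towards high levels and a drift towards low levels are therefore different findings about the algorithm. With the indicator alone, the study could report no change in success across infusions and leave the reader unable to tell whether exposure had moved.

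**Working it through.** **The plan's own figure.** Section 9.3 gives a 95% interval for 50 infusions at 80% success. The Wald formula reproduces it: 0.80 ± 1.96 × √(0.80 × 0.20 / 50) = 0.689 to 0.911, width 0.22. This concerns the primary estimate. The documents give no power or sample size for Aim 1b.

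**Inputs from the documents.** Window 50–80 µM; target 65 µM (2.4); 80% success (1.3, 9.3); 50 infusions (9.2, 9.3); up to 4 infusions per patient (4.1).

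**Assumptions not in the documents.**
- Levels are normal, with the SD set so that 80% fall in the window at mean 65: SD = 15 / 1.2816 = 11.7 µM (range tried 10 to 15).
- Within-patient correlation is 0.3 (range 0 to 0.5).
- The test is two-sided at 5%.
- The base layout is 13 patients × 4 infusions = 52, with the mean rising linearly.

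**Success rate.** P(success) = Φ((80 − m)/SD) − Φ((50 − m)/SD).

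| Mean, first to last (µM) | Success | Share above 80 µM |
|---|---|---|
| 60 to 70 | 76% to 76% | 4% to 20% |
| 65 to 75 | 80% to 65% | 10% to 33% |
| 65 to 80 | 80% to 49% | 10% to 50% |
| 75 to 85 | 65% to 33% | 33% to 67% |

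The zero change from 60 to 70 follows from symmetry and holds at any SD. For 65 to 75 the fall in success is 10 points at SD 15 and 18 points at SD 10. A lognormal check (geometric mean 63.2 µM, 80% in the window) agrees: a 25% rise straddling the centre leaves success at 72%, and a 10% rise from the centre lowers it from 80% to 74%.

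**Power on the level, 13 × 4, 65 to 75.** Slope per infusion = 10/3 = 3.33 µM. For infusions 0 to 3, the sum of squares about the mean is 5. The variance of one patient's slope is 11.7² × (1 − 0.3) / 5 ≈ 19.2. The standard error of the mean slope is √(19.2/13) = 1.21, so the non-centrality is 3.33/1.21 = 2.74 on 12 degrees of freedom, and power is 71%. At correlation 0 and 0.5 it is 56% and about 84%.

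**Power by simulation, correlation 0.3.** Per-patient slopes or differences were tested with a t reference. Test size was about 5% on both scales.

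| Layout | Rise (µM) | Indicator | Level |
|---|---|---|---|
| 13 × 4 | 65 to 75 | 14% | 71% |
| 13 × 4 | 60 to 70 | 5% | 71% |
| 25 × 2 | 65 to 75 | 21% | 93% |
| 50 × 2 | 65 to 75 | 41% | >99% |
| 25 × 2 | 65 to 80 | 63% | >99% |
| 13 × 4 | 75 to 85 | about 43% | about 72% |
| 25 × 2 | 75 to 85 | about 68% | about 93% |

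Fitting actual GEE trend models (25 patients × 4, 300 runs) gives the same ordering: 26% against 96% for 65 to 75, and 3% against 96% for 60 to 70.

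**The case against.** Aim 1b asks about the incidence of success, which is the primary outcome and the subject of the hypothesis. When the mean moves from 60 to 70 µM, success does not change, so 5% rejection is the correct answer to the aim's own question. This stands. A reader might infer that the planned GEE is wrong or fails its stated aim, and the documents do not support that. The gap is in what the aim leaves unexamined.

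A reader might also infer that any rise is hidden. That is not so. Rises from 65 to 80 µM or from 75 to 85 µM lower the success rate noticeably. Patients selected for risk of delayed clearance need not be centred on 65 µM, which is the case most favourable to the concern.

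The study may also be larger than 52 infusions. Section 9.2 counts only infusions needing an adjustment, and section 9.1 ties the sample size to each patient's first cycle. With 50 patients × 2 infusions, indicator power for 65 to 75 is 41%. This also stands, although the level remains well ahead.

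The 24-hour level follows rate reductions triggered at 2 and 6 (or 8) hours. Falling clearance might therefore appear as more reductions with an unchanged level. A free drift of 10 µM is an assumption, and the level is best read beside the dose given.

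Finally, section 2.1 reports variability between administrations and does not report a rise. Harm is followed directly through adverse events, creatinine and the stopping rules. Aim 1b is exploratory, and no decision depends on it.

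**Conclusion.** The concern holds in a limited form. The planned analysis of change across infusions carries no direction and is insensitive to shifts of about 10 µM or less near the 65 µM target. In the base case its power is about 14%, against 71% (56% to 84% over correlation 0 to 0.5) on a level that is already recorded. It has no sensitivity at all when the mean moves symmetrically across the window's centre. Larger or off-centre rises, and a larger study, narrow the gap without closing it in the cases run.

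The sizes rest on the assumed normal shape, SD, correlation and number of repeat infusions, none of which the documents give. The cancellation rests only on a symmetric distribution of constant spread and a two-sided window. The primary estimate and its interval are unaffected. This is a worthwhile supplement to an exploratory aim.

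**What to change.** In section 9.1 (Aim 1b) and section 9.3 (Analysis 1b and 1c):

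- Keep the binary GEE as the Aim 1b analysis.
- Add, as supplementary, a linear mixed model of the log 24-hour level on infusion number with a patient random intercept. Report the geometric mean ratio per infusion with a 95% CI.
- Report by infusion the proportions below 50, within 50–80 and above 80 µM, so that direction is visible.
- Show the total methotrexate given by infusion alongside, because rate reductions during the infusion affect the level.

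A model of absolute distance from target, such as |log(level/65)|, is not worth adding. In the 13 × 4 layout its power is about 11% for 65 to 75 µM and 6% for 60 to 70 µM, no better than the indicator's 14% and 5%.

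The cost is a short change to the statistical section and one extra exploratory model with a residual check on the log scale. No extra samples, patients or changes to treatment are needed.

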### 1.2 Secondary Aims

- 1.2.1 To determine the incidence of the following side effects in high risk patients receiving high dose methotrexate as a 24 hour infusion: nephrotoxicity, neurotoxicity, mucositis, hepatotoxicity, and myelosuppression.
- 1.2.2 To describe host polymorphisms that may identify risk of methotrexate toxicity or success of this institutional protocol.
- 1.2.3 To describe predictors of successfully achieving an optimum concentration of methotrexate at the end of a 24 hour infusion of HDMTX in patients at high risk of drug toxicity treated with this individualized high dose methotrexate protocol.

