### 2.3.1 Nephrotoxicity

As methotrexate is excreted nearly exclusively by the kidneys, methotrexate induced nephrotoxicity is a serious potential complication of treatment. The two main mechanisms of methotrexate induced nephrotoxicity involve damage to the renal tubules via either a direct toxic effect or as a result of the precipitation of methotrexate metabolites. The two main methotrexate metabolites, 7-hydroxymethotrexate (7-OH-MTX) and 2,4-diamino-N-methylpteroic acid (DAMPA), are at least six times less soluble at acidic pH than methotrexate. This decreased solubility prompted alkalinization of the urine to be a major component of methotrexate supportive care. In addition, alkalinization forces the ionization of methotrexate, a weak acid, making it more water soluble, preventing precipitation and trapping unchanged cleared methotrexate in urine for efficient elimination.

In patients receiving HDMTX, 1.8% will experience renal dysfunction resultant from HDMTX. This high risk group of patients has a mortality rate of 4.4%, greater than the mortality rate of 0.8% among patients who did not develop HDMTX induced renal dysfunction.

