### 2.3.2 Neurotoxicity

Methotrexate toxicity can lead to severe neurological sequelae. Among children treated with methotrexate, 3-11% will experience either transient or chronic symptoms of neurotoxicity such as: seizures, hemiparesis, aphasia, headache, and altered mental status. However, up to 76% of patients treated with HDMTX demonstrate leukoencephalopathic changes on magnetic resonance imaging (MRI). The prevalence of leukoencephalopathy increases with each subsequent course of HDMTX. Among patients who developed leukoencephalopathy following HDMTX, 10-56% had their symptoms recur when re-challenged with HDMTX.

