#### 4. TREATMENT PLAN

#### 4.1 Overview of Treatment Plan

Our prospective study will enroll patients who will receive HDMTX given as a 5g/m² 24-hour infusion. Enrolled patients will be receiving HDMTX as determined by their primary provider. Patients are eligible to be enrolled at any time point during their treatment course, and may participate during any one or more of their multiple HDMTX administrations.

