The interventions in this protocol occur at the 2 and 6 hour (or 8 hour if the 2 hour level was  $\geq 100 \mu M$ ) time points. After the 24hr HDMTX infusion is complete, the individualized protocol will end and patients will remain on study but be off of the protocol therapy. After this time, management of MTX levels will continue according the treating physician's discretion using standard supportive care guidelines. This is elaborated below in Appendix B, suggested supportive care guidelines based on the COG algorithm. Interventions for toxicity are at the discretion of the treating provider as patients will be off treatment protocol at the 24hr time point. Glucarpidase should be administered based on the treating physician's discretion, with the recommendation that it be administered prior to the development of grade 4 nephrotoxicity and prior to 96 hours after the start of the HDMTX infusion. Administration of CPDG2 after these time points have been shown to be statistically associated with the development of  $\geq$  grade 4 toxicity.

Patients may be re-enrolled on this protocol therapy again for subsequent HDMTX infusions without the need for re-consent. In order to re-enroll, call the study coordinating center as outlined in Section 3.1 PRIOR to the cycle in which the dose modification protocol will be implemented.

The active length of study participation for each patient is 4 weeks after the last high-dose methotrexate infusion or until the next cycle of chemotherapy begins (which ever occurs first). Therefore, the maximum amount of active time on study would be 2.5 months. This would include 4 doses of HDMTX given every other week plus a 4 week follow-up period to assess for side effects.

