#### 9.2 Patient Accrual and Expected Duration of Trial

Patients will be continually accrued until a target of 50 methotrexate infusions requiring any protocolprescribed dose adjustments are reached. The expected duration of accrual for the trial is 2-2.5 years.

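### Aim 1.2.1 asks for toxicity incidence in patients, but Section 9.1 states only a per-infusion frequency and no patient-level measure is defined

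*Combined protocol and SAP*

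**What the plan says.** Section 1.2.1 sets the aim: "To determine the incidence of the following side effects in high risk patients receiving high dose methotrexate as a 24 hour infusion". The five side effects are nephrotoxicity, neurotoxicity, mucositis, hepatotoxicity and myelosuppression.

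Section 9.1, Aim 2a, gives the analysis: "Calculate the frequency of adverse effects after each infusion". The same paragraph plans GEE for success over multiple cycles and adds: "This method will also be applied to the frequency of adverse events and to the assessment of factors associated with outcome". Section 9.3 repeats this. Neither section defines a patient-level toxicity measure.

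Section 5.7 also plans a summary of the incidence of treatment-emergent adverse events, without a denominator, and a by-patient listing of serious adverse events.

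On exposure, Section 4.1 says that patients "may participate during any one or more of their multiple HDMTX administrations". It describes the longest participation thus: "This would include 4 doses of HDMTX given every other week plus a 4 week follow-up period to assess for side effects". Section 7.1.1 ends protocol therapy for renal or neurologic toxicity of grade 3 or higher. Section 9.2 counts infusions, not patients: "Patients will be continually accrued until a target of 50 methotrexate infusions requiring any protocolprescribed dose adjustments are reached". The number of patients and the mean number of infusions per patient are not stated.

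**The concern.** The aim and its analysis use different units. Incidence in patients is most naturally the share of patients who have the toxicity while on study. A frequency after each infusion has infusions as its denominator. The two agree only when every patient has one infusion.

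At stake is how the safety result is read. A clinician deciding whether to offer this algorithm wants to know how many high-risk patients come to harm over the course. A per-infusion figure will usually be lower, and without patient counts the reader cannot convert it. Removal for severe renal or neurologic toxicity adds to this: patients who tolerate treatment go on supplying event-free infusions to the denominator, while those who do not stop contributing.

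**Working it through.** **The plan's own figure.** The documents give no design figure for toxicity. The only stated precision is for the success rate in Section 9.3: 0.80 ± 1.96 × √(0.80 × 0.20 / 50) = 0.80 ± 0.111, that is 0.689 to 0.911, width 0.222. This reproduces the stated 69% to 91% and 0.22, but has no bearing on toxicity.

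**Inputs.** Infusions per patient, m: 1 to 4 (Section 4.1). Per-infusion risk, q: illustrative values. Of these, 1.8% and 11% are figures that appear in Sections 2.3.1 and 2.3.2, used here only to span a range; 5%, 20% and 30% are assumed.

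**Step 1, independent infusions, same m for all.** Patient risk = 1 − (1 − q)^m. For q = 1.8% and m = 4: 1 − 0.982⁴ = 7.0%, and 7.0 / 1.8 ≈ 3.89 (from unrounded values). The ratio to q is in brackets.

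| q per infusion | m = 1 | m = 2 | m = 3 | m = 4 |
|---|---|---|---|---|
| 1.8% | 1.8% (1.00) | 3.6% (1.98) | 5.3% (2.95) | 7.0% (3.89) |
| 5% | 5% (1.00) | 9.8% (1.95) | 14.3% (2.85) | 18.5% (3.71) |
| 11% | 11% (1.00) | 20.8% (1.89) | 29.5% (2.68) | 37.3% (3.39) |
| 20% | 20% (1.00) | 36.0% (1.80) | 48.8% (2.44) | 59.0% (2.95) |
| 30% | 30% (1.00) | 51.0% (1.70) | 65.7% (2.19) | 76.0% (2.53) |

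**Step 2, correlated infusions, m = 4.** Beta-binomial with assumed within-patient correlation ρ, a = q(1 − ρ)/ρ and b = (1 − q)(1 − ρ)/ρ. Patient risk = 1 − Π (b + j)/(a + b + j), j = 0 to 3. For q = 1.8% and ρ = 0.5: 1 − 0.982 × 0.991 × 0.994 × 0.9955 = 3.7%, ratio 2.06.

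| q per infusion | ρ = 0.1 | ρ = 0.3 | ρ = 0.5 |
|---|---|---|---|
| 1.8% | 3.39 | 2.63 | 2.06 |
| 5% | 3.25 | 2.55 | 2.01 |
| 20% | 2.67 | 2.20 | 1.81 |
| 30% | 2.34 | 1.99 | 1.68 |

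**Step 3, events that end protocol therapy.** Suppose removal under Section 7.1.1 is lasting (Section 4.1 does not say whether a removed patient may re-enrol). Then each patient has at most one such event. With E events, the patient rate is E / patients and the infusion rate is E / infusions, so their ratio is the mean number of infusions per patient. Repeat events cannot pull this ratio toward 1.

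**Step 4, illustration.** Assume 50 infusions in all and two events in different patients. The per-infusion frequency is 2/50 = 4%. The patient proportion is 2/50 = 4% with one infusion each, 2/25 = 8% with two, 2/17 = 11.8% with about three and 2/13 = 15.4% with about four.

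**The case against.** Several points on the other side are sound.

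- A reader might infer that the plan pools correlated infusions naively. It does not: GEE is planned for adverse-event frequency. But GEE corrects the standard error. Its estimate is still a probability per infusion.
- A reader might infer that patient-level safety is absent. It is under-specified: Section 5.7 plans an incidence summary and a by-patient listing of serious events, and the toxicity stopping rules in Section 8.1 count patients. A listing is not an incidence estimate, however, and the summary has no stated denominator.
- A reader might set the per-infusion result against the background statements "In patients receiving HDMTX, 1.8% will experience renal dysfunction resultant from HDMTX" and "Among children treated with methotrexate, 3-11% will experience either transient or chronic symptoms of neurotoxicity", and infer that such a comparison is planned or has been made impossible. The documents support neither. The only planned external comparison is of allele frequencies, and events are collected by course (Section 5.7), so a patient-level rate can be derived. The exposure behind the background rates is not given.
- A reader might infer a fourfold understatement. Four is the ceiling set by the maximum number of doses. Eligibility partly on prior toxicity (Section 3.2.2) makes independence doubtful.
- The aim's reference to patients may only name the population, and the analysis may mean frequencies by infusion number, each with patients as denominator. That is a fair reading, but even then no figure covers the on-study course.

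What stands is that no patient-level incidence is defined for an aim worded in patients.

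**Conclusion.** The mismatch is real and of moderate weight: it affects a secondary, descriptive aim and can be repaired from data already being collected. With equal infusions per patient, the risk to a patient over the on-study course exceeds the per-infusion frequency by a factor of 1 with one infusion, 1.7 to 2.0 with two, and 1.7 to 2.1 with four at an assumed correlation of 0.5. It is at most about 3.9 for a 1.8% event with four independent infusions. Where the trial will fall is unknown, because the plan does not state the mean number of infusions.

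The direction also rests on an assumption: that patients at higher risk do not contribute more infusions. In an extreme case, one patient with events at all four infusions and four patients with one event-free infusion each give 4/8 = 50% per infusion but 1/5 = 20% per patient. For severe renal and neurologic events, Section 7.1.1 pushes the other way. The two measures answer different questions, so both are needed.

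**What to change.** In Section 9.1, Aim 2a, and to match in Section 9.3:

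- For each of the five toxicities, report the proportion of patients with at least one qualifying event over all on-study infusions, with an exact 95% interval. Take the grades from Section 5.7: grade 3 or higher for mucositis, myelosuppression and hepatotoxicity, any grade for neurotoxicity and nephrotoxicity.
- Show the number of patients and the distribution of infusions per patient as a description of exposure. Do not present rates by number of infusions received as risks: that number can itself depend on toxicity through Section 7.1.1.
- Keep the GEE per-infusion frequency alongside.
- In Section 5.7, state patients as the denominator of the adverse-event incidence summary.

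The cost is SAP wording and one table, with no new data. The patient-level interval rests on fewer units and is wider. With no events, the exact upper limit is 1 − 0.025^(1/n): 7.1% for 50 patients, 13.7% for 25 and 24.7% for 13 (the patient counts of the illustration). The crude proportion also mixes patients with one to four infusions of exposure, which is why the per-infusion figure should stay beside it.
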